## 10. Medical and Surgical History and Continuing Medical Condition

Medical and surgical history, continuing medical conditions will be coded using Medical Dictionary for Regulatory Activities central coding dictionary, Version 22.0 (MedDRA 22.0), and summarized by system organ class (SOC) and preferred term (PT) for the RAN. Continuing medical condition was identified the items with 'Ongoing with treatment' or 'Ongoing without treatment' status in the Medical History page of the eCRF. SOCs will be presented alphabetically; PTs will be sorted within SOC in descending order of subject frequency across both treatments (Total). If the frequency of the PT is tied, the PTs will be sorted alphabetically.

## 11. Medications and Procedures

### Medications

Prior and/or concomitant medications will be coded using WHO DRUG dictionary DDE B2 format Mar 01, 2018 and Anatomical Therapeutic Chemical (ATC) Classification.

See Appendix 1 for the handling of partial dates for medications, in the case where it is not possible to define a medication as prior or concomitant, the medication will be classified by the worst case; i.e. concomitant.

- 'Prior' medications are medications which started prior to and finished prior to the first dose of study drug.
- 'Concomitant' medications are medications which started on or after the first dose of study drug, or started prior to the first dose of study drug and ended on or after the first dose of study drug or are ongoing at the end of the study.

A medication will be considered as either 'Prior' or 'Concomitant'.

Prior medication and concomitant medications will be summarized by ATC pharmacological sub-class (4th level) for the SAF. ATCs will be presented alphabetically; PTs will be sorted within ATC in descending order of subject frequency across both treatments (Total). If the frequency of the PT is tied, the PTs will be sorted alphabetically. All medications used will be listed.

---

Document:

Author:

Version Number:

Version Date:

Final v1.0

10Sep2019

Template No: CS\_TP\_BS016 Revision 4

Effective Date: 01Apr2016

Reference: CS\_WI\_BS005

## Procedure

Prior cancer-related surgery or procedure, as reported on the eCRF 'Prior cancer-related surgery or procedure' page, will be coded using MedDRA 22.0, and summarized by SOC and PT for the SAF. SOCs will be presented alphabetically; PTs will be sorted within SOC in descending order of subject frequency across both treatments (Total). If the frequency of the PT is tied, the PTs will be sorted alphabetically. Details of the cancer-related surgery or procedure will be listed in listings.

See Appendix 1 for the handling of partial dates for procedure.

## 12. Study Medication Exposure

### 12.1. STUDY DRUG ADMINISTRATION

Duration of exposure to study drug in days, number of administrations and total dose administered (mg), dose intensity (mg/m^2/day), relative dose intensity (RDI), any dose interruption will be summarized by treatment group with descriptive statistics using the SAF.

Exposure duration (days) will be calculated according to the following algorithm.

- If the last date the patient took study drug was known;
  - Exposure duration (days) = last study drug date – first study drug date + 1,
- If the last date the patient took study drug was unknown, but the visit that the patient took last study drug was known;
  - Exposure duration (days) = the visit date of last study drug – first study drug date + 1,
- If the last date the patient took study drug was unknown and the visit that the patient took last study drug was also unknown;
  - If the last visit before the patient discontinued or withdrew is after Week 4 visit OR the patient completed the study, then Exposure duration (days) = date of Week 4 visit – first study drug date + 1
  - If the last visit before the patient discontinued or withdrew is before Week 4 visit, then Exposure duration (days) = the last visit date – first study drug

---

Document:

Author:

Version Number:

Version Date:

Final v1.0

10Sep2019

Template No: CS\_TP\_BS016 Revision 4

Effective Date: 01Apr2016

Reference: CS\_WI\_BS005

date + 1

Interruptions, compliance, and dose changes are not taken into account for duration of exposure.

Dose intensity is derived from the following definitions:

- Dose Intensity (mg/ m^2/day) = sum of actual dose level administered (mg/ m^2) / duration of exposure (days), where the actual dose level administrated = administrated actual total dose (mg) in that cycle / BSA for dose calculation in that cycle (m^2) from electronic case report form (eCRF).

RDI is based on the actual dose intensity and the planned dose intensity and will be calculated as follows:

- $RDI (\%) = \frac{\text{actual dose intensity}}{\text{planned dose intensity}} \times 100$

Where the planned dose intensity can be calculated following below algorithm:

Planned dose intensity (mg/ m^2/day) = 4\*375(mg/m^2) / 28

Study drugs administration data will be listed.

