4.0 STUDY TREATMENTS

4.1 Treatments Administered

Following randomization, SAIT101 or MabThera[®] treatment will be administered as an i.v. infusion once a week for 4 weeks, at a standard dose of 375 mg/m² body surface area. If the patient's weight changes by more than 10% before the next infusion, then BSA should be recalculated. Cycle 1 Day 1 study drug must be administered within 0 to 4 days after randomization.

Both treatments are anti-CD20+ antibody medications.

For study drug administration details, please see Section 4.5. For pre-medication administration details, please see Section 4.4 and Appendix 8.

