#### **4.5. PER PROTOCOL SET [PPS]**

The Per Protocol set (PPS) consists of all FAS patients who have the diagnosis of FL confirmed by central pathology review and have no major protocol deviations that would significantly impact the study outcome, as determined by blinded medical review. A patient may be excluded from the PPS for, but not limited to, any of the following conditions.

- Patient did not meet inclusion/exclusion criteria
- Infusion of wrong study drug occurred
- Patient did not receive all 4 infusions of study drug (Days 1, 8, 15, and 22)
- Intake of prohibited treatment, this is subject to evaluation of the clinical relevance of the treatment intake

Major protocol deviations and/or the situation that lead to exclusion from the PPS will be specified and authorized prior to unblinding the treatment arms. Efficacy endpoints will also be summarized on the PPS.

The Per Protocol set for exploratory analysis (PPSEXP) consists of all the PPS patients who had their tumor measured by positron emission tomography computerized tomography (PET-CT) scan.

---

Document:

Author:

Version Number:

Version Date:

Final v1.0

10Sep2019

Template No: CS\_TP\_BS016 Revision 4

Effective Date: 01Apr2016

Reference: CS\_WI\_BS005

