$C_{max,w4}$	Maximum serum concentration ( $\mu\text{g/mL}$ ) over the 4 th dosing interval on Week 4, obtained directly from the observed concentration versus time data. This parameter will only be reported if the end-of-infusion concentration is available and evaluable.
$t_{max,w1}$	Time of maximum concentration (h) over the 1 st dosing interval on Week 1, obtained directly from the observed concentration versus time data. Calculations will follow conventions of $C_{max,w1}$ .
$t_{max,w4}$	Time of maximum concentration (h) over the 4 th dosing interval on Week 4, obtained directly from the observed concentration versus time data. Calculations will follow conventions of $C_{max,w4}$ .
$C_{trough}$	Concentrations at predose on Days 8, 15, and 22 ( $\mu\text{g/mL}$ ) and the time equivalent to the predose on Day 29, obtained directly from the observed concentration versus time data.
RAUC	Accumulation ratio, calculated for $AUC_{0-168}$ as $(AUC_{0-168,w4}/AUC_{0-168,w1})$ .
$RC_{max}$	Accumulation ratio, calculated for $C_{max}$ as $(C_{max,w4}/C_{max,w1})$ .

The following deviations related to time of sample collections will be considered for calculation of the above parameters.  $AUC_{0-168}$  or/and  $C_{max}$  will be calculated and reported, but not included in summary and inferential statistical analyses if:

- The end of infusion sample is collected more than 10 minutes early or after the end-of-infusion,  $AUC_{0-168}$  and  $C_{max}/t_{max}$  will be calculated and reported, but not included in summary and inferential statistical analyses.
- 168 hour postdose sample (i.e. predose of following infusion) is collected more than 1 calendar day early or late for Week 1 and Week 4,  $AUC_{0-168}$  will be calculated and reported, but not included in summary and inferential statistical analyses. The trough concentration on Day 29 will not be included in any summaries if the sample is collected more than 1 calendar day early or late.
- Dose on Week 4 is more than 1 calendar day outside the scheduled time, data will be carefully evaluated if inclusion of  $AUC_{0-168}$ ,  $C_{max}$ ,  $t_{max}$ , and trough concentration on Day 29 in summaries and/or inferential analyses is warranted.
- Dose is missed either on Week 2 and/or Week 3, Week 4 PK parameters will be calculated and reported but not included in summaries and/or inferential analyses.

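### SAP 12.1 divides the actual dose by 22 days on schedule but the planned dose by 28, so a fully compliant course scores a relative dose intensity of 127%

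*SAP*

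**What the plan says.** SAP 12.1 summarises exposure duration, number of administrations, total dose in mg, dose intensity in mg/m²/day, RDI and dose interruptions by treatment group in the safety set. When the last dosing date is known, the duration is "Exposure duration (days) = last study drug date – first study drug date + 1". The fallback rules for an unknown date also end in + 1. The section adds that "Interruptions, compliance, and dose changes are not taken into account for duration of exposure".

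Actual dose intensity is the sum of the mg/m² received divided by that duration. Planned dose intensity is fixed at 4 × 375 mg/m² divided by 28. The SAP states that "RDI is based on the actual dose intensity and the planned dose intensity", and RDI is the first as a percentage of the second.

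Protocol 4.1 gives the regimen as "infusion once a week for 4 weeks, at a standard dose of 375 mg/m² body surface area". Protocol Table 1 and SAP 4.5 place the infusions on Days 1, 8, 15 and 22, and Table 1 allows ± 1 day around Day 22.

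**The concern.** A ratio of actual to planned intensity should read 100% when the plan is followed exactly. That requires both intensities to cover the same stretch of time. Here the planned figure spans four 7-day intervals, while the actual figure ends on the day of the last infusion and omits the fourth interval. SAP 13.2 treats that interval as a full week: it takes the Week 4 AUC to 168 hours after the dose.

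Readers of an exposure table will judge RDI against 100%. Under this derivation a compliant patient appears to be 27% over plan, and a patient who received about a fifth less than planned over the 22 days appears to be on plan. Early stopping after full doses pushes the value up when it should show less drug delivered. Of the summaries listed in 12.1, RDI is the only one that compares delivery with plan.

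**Working it through.** The SAP states formulas but no numerical RDI, so there is no printed figure to reproduce. The natural benchmark is 100% for a full course on schedule.

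**Inputs.** 375 mg/m² per infusion, four infusions, total 1500 mg/m² (Protocol 4.1); infusions on Days 1, 8, 15 and 22, the last with a ± 1 day window (Protocol Table 1, SAP 4.5); the duration, intensity and RDI formulas (SAP 12.1).

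**Planned intensity.** 1500/28 = 53.57 mg/m²/day.

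**Full course on schedule.** Duration = 22 − 1 + 1 = 22 days. Actual intensity = 1500/22 = 68.18 mg/m²/day. RDI = 68.18/53.57 = 28/22 = 127.3%. With the fourth infusion on Day 21 it is 28/21 = 133.3%; on Day 23 it is 28/23 = 121.7%. Four full doses score 100% only when the last falls on Day 28, six days late.

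**Dose that scores 100% over 22 days.** 22 × 53.57 = 1178.6 mg/m², and 1178.6/1500 = 78.6% of plan. Three full infusions (1125) plus 53.6 mg/m² of the fourth (14.3% of 375) would do it. Receiving 90% of plan scores (1350/22)/53.57 = 114.5%.

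**Other patterns of full doses**, under the SAP rule and two alternative denominators:

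| Infusion days | mg/m² | SAP duration | RDI, SAP rule | RDI, last − first + 7 | RDI, max(28, last − first + 7) |
|---|---|---|---|---|---|
| 1, 8, 15, 22 | 1500 | 22 | 127.3% | 100% | 100% |
| 1, 8, 15 | 1125 | 15 | 140% | 100% | 75% |
| 1, 8 | 750 | 8 | 175% | 100% | 50% |
| 1 | 375 | 1 | 700% | 100% | 25% |
| 1, 8, 22 or 1, 15, 22 | 1125 | 22 | 95.5% | 75% | 75% |
| 1, 15 | 750 | 15 | 93.3% | 66.7% | 50% |
| 1, 22 | 750 | 22 | 63.6% | 50% | 50% |

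The inflation therefore comes from doses dropped at the end. RDI falls when a middle dose is skipped and a later one given, a case SAP 13.2 foresees ("Dose is missed either on Week 2 and/or Week 3"). A single interrupted first infusion exceeds the full-course score of 127.3% only if more than 68.18 mg/m² (18.2% of 375) went in, and falls below 100% if less than 53.57 mg/m² (14.3%) did.

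**A partial repair that fails.** Changing only the planned denominator to 22 days gives 100% for the full course, but early stopping still scores 75/68.18 = 110%, 93.75/68.18 = 137.5% and 375/68.18 = 550%.

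**The case against.** The strongest reply is that little depends on RDI. It is descriptive, has no threshold attached and feeds no test. Per-protocol exclusion for incomplete treatment counts infusions directly, and SAP section 17 rules out statistical comparison of safety data. A reader who sees 127% can also see four administrations over 22 days. All of this is correct and limits the weight of the point. It does not repair the derivation. Total dose is reported in mg, so it cannot be read directly against 375 mg/m², and the number of administrations does not show how much of an infusion was given.

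A second reply is that the 78.6% patient is contrived, because Protocol 4.13 and Appendix 8 do not permit dose changes. Such a patient could arise only from an interrupted infusion or a deviation, and the documents give no rate for either. That stands: the example shows where the 100% mark falls, not how often it would matter. The 127.3% result needs no such case.

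Third, 22 days holds only for on-schedule dosing. Protocol 4.8 and 4.9 allow delayed or held infusions, which lengthen the denominator, so completed courses can score below 121.7%. That also stands.

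Finally, the mg/m²/day summary agrees with its own stated definition. This is true, but it sits beside a planned value of 53.57 in the same units, and a course delivered exactly as planned will show 68.18.

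**Conclusion.** The derivation is wrong as written. A full on-schedule course scores 127.3% (121.7% to 133.3% within the ± 1 day window), and full-dose early stoppers score 140%, 175% or 700%. These figures rest only on the SAP's formulas and the planned infusion days. Nothing in 12.1 adds the last interval or caps RDI, and SAP 2.6 does not address it.

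The fault is limited to the dose intensity and RDI summaries. The same rule applies in both arms, and neither the equivalence test on response rate nor the PK comparison uses it. No arm-level effect can be stated, because the documents give no rate of stopping infusions. A common rule keeps the arms comparable only if their stopping patterns are alike: for each 1% of an arm stopping after one full dose in place of four on schedule, that arm's mean RDI rises by (700 − 127.3)/100 = 5.7 points. The derivation should be corrected; the trial's conclusions do not depend on it.

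**What to change.** Put both intensities on one time base and say what RDI measures. Keep planned intensity at 1500/28 and choose one of two denominators for actual intensity:

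- **Rate while on treatment:** last dose date − first dose date + 7. A full on-schedule course scores 100% (Day 21: 1500/27 against 53.57 = 103.7%; Day 23: 1500/29 = 96.6%). Patients who stop early but were on schedule also score 100%, so this version does not show under-delivery of the course.
- **Delivery of the planned course:** the larger of 28 and last dose date − first dose date + 7. Four, three, two and one consecutive full doses score 100%, 75%, 50% and 25%.

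Use the same denominator for the mg/m²/day summary. Take the last dose date from the known-date and fallback rules already in 12.1, and leave the exposure-duration summary as it is. The cost is one derivation line and one explanatory sentence in the SAP. No new data are needed, and no dosing rule is affected.

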## 12.2. INFUSION PRE-MEDICATION

'Infusion pre-medication' is either corticosteroids, analgesic or antipyretic, or anti-histamine administrated before the start of each study drug infusion.

Infusion pre-medication data will be listed.

## 13. Pharmacokinetics

### 13.1. SERUM CONCENTRATION DATA

A listing of PK blood sample collection times and derived sampling time deviations, as well as rituximab concentrations will be provided. Serum concentrations of rituximab will be listed and summarized by treatment and by study week, study day, and nominal time point using appropriate descriptive statistics, such as number of data (n), mean, standard deviation (SD), percentage coefficient of variation (CV%), minimum, median, and

---

Document:

Author:

Version Number:

Version Date:

Final v1.0

10Sep2019

Template No: CS\_TP\_BS016 Revision 4

Effective Date: 01Apr2016

Reference: CS\_WI\_BS005

Copyright © 2009, 2010, 2012, 2016 Quintiles Transnational Corp. All rights reserved.

The contents of this document are confidential and proprietary to Quintiles Transnational Corp. Unauthorized use, disclosure or reproduction is strictly prohibited.

maximum. Concentrations excluded from analyses will be flagged in the listings. Unscheduled assessments will be listed but not included in summary statistics. Analyte concentrations which fall below limit of quantification (BLQ) will be set to zero and missing concentration values will be omitted for all concentration summaries. For PK parameter summaries,  $C_{\text{trough}}$  values that are BLQ will be treated as the lower limit of quantification (LLOQ)/2.

Plots of individual and mean serum rituximab concentration-time profiles will be presented by treatment, Week/Day, and nominal time point on both linear and semi-logarithmic scales.

Additional graphical presentations of PK data may be added at the discretion of the PK scientist.

## 13.2. PHARMACOKINETIC PARAMETERS

For PK parameter calculations on Week 1, predose samples that are BLQ or missing will be assigned a numerical value of zero. Any anomalous concentration values observed at predose over the 1st dosing interval will be identified in the study report and used for the computation of PK parameters. Pharmacokinetic parameters will be computed if the anomalous concentration is not greater than 5% of the observed maximum concentration ( $C_{\text{max}}$ ). If the anomalous concentration is greater than 5% of  $C_{\text{max}}$ , the PK parameters for the given patient will be calculated and reported in the listing, but excluded from statistical summaries and analyses. On week 4, predose sample that is BLQ will be assigned a numerical value of zero. Missing predose sample will be set to missing.

The following PK parameters will be calculated for rituximab for each treatment by non-compartmental methods using actual elapsed time from dosing, if possible.

$AUC_{0-168,w1}$	Area under the serum concentration-time curve (AUC) over the 1 st dosing interval on Week 1 from time zero (predose) to the time prior to the 2 nd dose (168 hours postdose) ( $\mu\text{g}\cdot\text{h}/\text{mL}$ ), calculated by linear up/log down trapezoidal summation. This parameter will only be calculated if at least the 2 postdose concentrations (the end of infusion and Week 2 predose) are available and evaluable.
$AUC_{0-168,w4}$	Area under the serum concentration-time curve (AUC) over the 4 th dosing interval on Week 4 from time zero (predose) to 168 hours postdose ( $\mu\text{g}\cdot\text{h}/\text{mL}$ ), calculated by linear up/log down trapezoidal summation. This parameter will only be calculated if all 3 concentrations (predose, the end of infusion, and Week 5) are available and evaluable.
$C_{\text{max},w1}$	Maximum serum concentration ( $\mu\text{g}/\text{mL}$ ) over the 1 st dosing interval on Week 1, obtained directly from the observed concentration versus time data. This

---

Document:

Author:

Version Number:

Final v1.0

Version Date:

10Sep2019

Template No: CS\_TP\_BS016 Revision 4

Reference: CS\_WI\_BS005

Effective Date: 01Apr2016

	parameter will only be reported if the end-of-infusion concentration is available and evaluable.
$C_{max,w4}$	Maximum serum concentration ( $\mu\text{g/mL}$ ) over the 4 th dosing interval on Week 4, obtained directly from the observed concentration versus time data. This parameter will only be reported if the end-of-infusion concentration is available and evaluable.
$t_{max,w1}$	Time of maximum concentration (h) over the 1 st dosing interval on Week 1, obtained directly from the observed concentration versus time data. Calculations will follow conventions of $C_{max,w1}$ .
$t_{max,w4}$	Time of maximum concentration (h) over the 4 th dosing interval on Week 4, obtained directly from the observed concentration versus time data. Calculations will follow conventions of $C_{max,w4}$ .
$C_{trough}$	Concentrations at predose on Days 8, 15, and 22 ( $\mu\text{g/mL}$ ) and the time equivalent to the predose on Day 29, obtained directly from the observed concentration versus time data.
RAUC	Accumulation ratio, calculated for $AUC_{0-168}$ as $(AUC_{0-168,w4}/AUC_{0-168,w1})$ .
$RC_{max}$	Accumulation ratio, calculated for $C_{max}$ as $(C_{max,w4}/C_{max,w1})$ .

The following deviations related to time of sample collections will be considered for calculation of the above parameters.  $AUC_{0-168}$  or/and  $C_{max}$  will be calculated and reported, but not included in summary and inferential statistical analyses if:

- The end of infusion sample is collected more than 10 minutes early or after the end-of-infusion,  $AUC_{0-168}$  and  $C_{max}/t_{max}$  will be calculated and reported, but not included in summary and inferential statistical analyses.
- 168 hour postdose sample (i.e. predose of following infusion) is collected more than 1 calendar day early or late for Week 1 and Week 4,  $AUC_{0-168}$  will be calculated and reported, but not included in summary and inferential statistical analyses. The trough concentration on Day 29 will not be included in any summaries if the sample is collected more than 1 calendar day early or late.
- Dose on Week 4 is more than 1 calendar day outside the scheduled time, data will be carefully evaluated if inclusion of  $AUC_{0-168}$ ,  $C_{max}$ ,  $t_{max}$ , and trough concentration on Day 29 in summaries and/or inferential analyses is warranted.
- Dose is missed either on Week 2 and/or Week 3, Week 4 PK parameters will be calculated and reported but not included in summaries and/or inferential analyses.

$AUC_{0-168,w1}$  and  $AUC_{0-168,w4}$  will be considered as primary PK endpoints and the other parameters will be secondary.

---

Document:

Author:

Version Number:

Version Date:

Final v1.0

10Sep2019

Template No: CS\_TP\_BS016 Revision 4

Effective Date: 01Apr2016

Reference: CS\_WI\_BS005

All primary and secondary PK parameters will be listed and summarized by treatment and study week using n, mean, SD, standard deviation, CV%, minimum, median, maximum, and geometric mean, geometric CV%, except that  $t_{max}$  will be reported with n, minimum, median, and maximum only.

The additional following summaries of PK parameters will be generated:

- By treatment and region (EU, Other including US)
- By treatment and age category (18-60 years and >60 years)
- By treatment and sex
- By treatment and overall ADA status.

The geometric means of the primary PK parameters ( $AUC_{0-168,w1}$  and  $AUC_{0-168,w4}$ ) will be compared between SAIT101 and MabThera® using analysis of variance on the loge-transformed parameters with fixed effect for treatment. No covariates will be included. Least-squares geometric means will be presented for each treatment with corresponding 95% CIs. The ratio of least-squares geometric means (SAIT101/MabThera®) will be presented with corresponding 90% CIs. Pharmacokinetic similarity will be concluded if the ratio of least-squares geometric means falls between 80.00% and 125.00% for both primary parameters. Estimates and CI will also be provided for  $C_{max,w1}$ ,  $C_{max,w4}$ , and  $C_{trough}$  (Day 29) parameters using the same methods.

A sensitivity analysis will be performed for the above PK comparisons, in which the above comparison will be replicated, with the addition of the following covariates to the statistical model: age, sex, overall ADA status, body weight at baseline.

Scatter plots of individual and geometric mean primary PK parameters  $AUC_{0-168,w1}$ ,  $AUC_{0-168,w4}$ ,  $C_{max,w1}$  and  $C_{max,w4}$  will be presented. Additional, graphical presentations of PK data may be added at the discretion of the PK scientist, if further illustration of the PK results is deemed appropriate.

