Clinical chemistry: creatinine, alkaline phosphatase, total bilirubin, AST, ALT, total protein, albumin, calcium, BUN, phosphorus, uric acid, and electrolytes (sodium, potassium, chloride).
Hematology: hemoglobin, hematocrit, platelets, white blood cells with differentiation, and neutrophils (absolute counts).
Urinalysis: glucose, protein, blood and leukocytes.
- r To be performed by the local laboratory. Screening performed to confirm negative serology for HIV and HCV. HIV screening test will be performed according to local practice and local regulatory guidance. Patients who are confirmed positive and those who have active infections will be excluded from the participation in the study.
- s Screen all patients for HBV infection by measuring HBsAg and anti-HBcAb. Patients who are confirmed positive for chronic hepatitis B infection (defined as positive HBsAg serology) and those who have active infections will be excluded from the participation in the study. Patients with occult or prior hepatitis B infection (defined as positive total HBcAb and negative HBsAg) may be included if HBV DNA is <20 IU/mL (or 112 copies/mL) by PCR test. These HBV patients must be willing to undergo PCR HBV DNA testing (to be performed by the local laboratory) during study and may participate following consultation with a hepatitis expert regarding monitoring and use of HBV antiviral therapy, and provided that they agree to receive treatment as indicated. An HBV re-test will be performed at each study visit from Week 5 onwards, and at the discretion of the Investigator.
- t To be performed at screening unless obtained within 3 months prior to Day 1. TB screening test will be performed if required by local regulatory guidance or at the investigator's discretion. A chest X-ray will be required for all patients with a positive TB test to confirm there is no active TB.
- u Blood PK samples will be collected **from the PK/PD sub-population of patients only**. Please refer to information about sampling time points as below:
Days 1, 8, 15, and 22: 0 hours (pre-dose), and at the end of infusion (\pm 10 minutes windows)
For all other time points: Infusion start time on Day 1 (\pm 6 hours window)
- v Blood samples for CD19+ B-cell counts will be collected, **from the PK/PD sub-population of patients only**, at the same time points for PK sampling plus Weeks 36 and 52.

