#### **Pharmacokinetic/ Pharmacodynamic sub-population**

For PK, assuming a coefficient of variation (CV) of 38% in both  $AUC_{0-168}$ , based on Regazzi et al. 2005 and assuming no true difference between SAIT101 and MabThera® in this parameter, 60 evaluable patients per arm are required to yield 81% overall power for comparison of  $AUC_{0-168, 1}$  and  $AUC_{0-168, 4}$  between the test and comparator treatments, using the standard two one-sided testing procedures, a 5% significance level for each one-sided test (90% CI). To ensure 120 evaluable patients are available, a total of 134 patients will be randomized for the PK/PD sub-population.

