#### **4.8.1. DEVIATIONS RELATED TO PHARMACOKINETIC AND PHARMACODYNAMIC ANALYSIS**

Changes to procedures or events, which impact the quality of the PK and PD data, will be considered significant protocol deviations/events for the PK/PD analysis and will be described within the CSR body text. These changes or events will include any circumstances that could alter the evaluation of the PK and PD. Examples include, but may not be limited to, sample processing errors that lead to inaccurate bioanalytical results, and/or inaccurate dosing on the day of PK and PD sampling. In the case of a significant protocol deviation or event, PK and PD data collected during the affected treatment period will be excluded from the study results but will be included in the by-patient listings. Other changes to the procedures or events which do not impact the quality of the PK data will not be considered significant protocol deviations. A common example of a non-significant protocol deviation is deviations from blood sample collection times.

Deviations will be reviewed in a blinded manner prior to database lock. Based on this review, patients or PK/PD data points will be excluded from the analyses as deemed appropriate. Deviations or events with the potential to affect PK/PD results will be listed, as will the excluded data points.

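### The protocol allows the Week 5 PK sample on Day 29 ±3, but the SAP drops the fourth-dose AUC when that sample is more than 1 day off, so compliant patients leave a primary PK comparison

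*SAP*

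**What the plan says.** The schedule in Protocol Table 1 sets the fourth infusion at Day 22 ±1 and the Week 5 visit, which includes a PK sample, at Day 29 ±3. Footnote u covers PK samples at visits without an infusion: "For all other time points: Infusion start time on Day 1", with a ±6 hour window.

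SAP 13.2 makes the Week 5 concentration indispensable for AUC0-168,w4: "This parameter will only be calculated if all 3 concentrations (predose, the end of infusion, and Week 5) are available and evaluable". It then lists timing exclusions. If, for the Week 1 or the Week 4 interval, the "168 hour postdose sample (i.e. predose of following infusion) is collected more than 1 calendar day early or late", the AUC "will be calculated and reported, but not included in summary and inferential statistical analyses". The Day 29 trough is left out of all summaries on the same limit. AUC0-168,w1 and AUC0-168,w4 are the two primary PK endpoints, and PK similarity is concluded only if both meet 80.00-125.00%.

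On numbers, SAP 2.3 and Protocol 8.4 ask for 60 evaluable patients per arm to give 81% overall power, and the SAP adds: "To ensure 120 evaluable patients are available, a total of 134 patients will be randomized for the PK/PD sub-population".

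SAP 2.6, which lists changes from the protocol, does not mention the ±1-day rule. SAP 4.8.1 says: "A common example of a non-significant protocol deviation is deviations from blood sample collection times".

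**The concern.** A site can schedule the Week 5 visit exactly as Table 1 permits and still cost the trial a primary PK value. The other two sampling-time limits in SAP 13.2 match the protocol: end of infusion within 10 minutes, and the Week 1 168-hour sample within 1 day against Day 8 ±1. Only Week 5 is out of step, and SAP 2.6 is silent, which suggests an oversight.

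Blinded scheduling gives no clear reason to expect bias between arms, so the stake is precision. Similarity needs both AUCs, and the reserve is 134 − 120 = 14 patients (14/134 = 10.4%) for every cause of non-evaluability: missed doses, missing samples, PK-relevant deviations and visit timing together.

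**Working it through.** **1. Which permitted days fail.** SAP 13.2 does not say whether early or late is judged against nominal Day 29 or against 7 days after the actual fourth dose.

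Against nominal Day 29, the protocol permits Days 26-32 and the SAP keeps Days 28-30. Days 26, 27, 31 and 32 fail: 4 of 7.

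Against the actual dose, the SAP keeps intervals of 7 ±1 days:

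| Dose 4 on | Kept | Too early | Too late |
|---|---|---|---|
| Day 21 | 27-29 | 26 | 30, 31, 32 |
| Day 22 | 28-30 | 26, 27 | 31, 32 |
| Day 23 | 29-31 | 26, 27, 28 | 32 |

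Of 21 pairs, 9 are kept and 12 fail: 6 too early and 6 too late. The interval runs from 26 − 23 = 3 days to 32 − 21 = 11 days. The share of permitted days that fail is 4/7 on either reading.

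**2. Reproducing the stated power.** Inputs from Protocol 8.4 and SAP 2.3: CV 38%, true ratio 1, two one-sided tests at 5%, 60 per arm. Limits are ±ln(1.25) = ±0.2231.

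- Log-scale SD: σ = √ln(1 + 0.38²) = 0.367.
- Normal approximation for one AUC: 2Φ(0.2231 / (σ√(2/n)) − 1.645) − 1. At n = 60 this is 2Φ(3.33 − 1.645) − 1 ≈ 90.8%. The t-based version, integrated over the distribution of the estimated SD, gives 90.4%.
- Both AUCs, treated as independent: 0.904² = 81.7%, against 81% stated. The plan's figure reproduces.

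**3. Effect of losing fourth-dose AUCs.** The documents give no distribution of Week 5 visit days, so the loss is an assumption. Two starting points are shown, each used for both AUCs: 60 per arm otherwise evaluable, or all 67. Week 1 power is 90.4% and 93.6% respectively.

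| Assumed loss | From 60: n, w4 power, overall | From 67: n, w4 power, overall |
|---|---|---|
| 0% | 60, 90.4%, 81.7% | 67, 93.6%, 87.7% |
| 10% | 54, 86.4%, 78.1% | 60, 90.4%, 84.6% |
| 20% | 48, 81.0%, 73.2% | 54, 86.4%, 80.9% |
| 30% | 42, 73.6%, 66.5% | 47, 79.9%, 74.8% |
| 4/7 (even spread) | 26, 39.4%, 35.6% | 29, 47.8%, 44.8% |

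Overall is the product of the Week 1 and fourth-dose powers, e.g. 0.904 × 0.810 = 73.2%. Correlation between the AUCs raises it slightly: for a 20% loss from 60 per arm, simulation gives 74.6% at correlation 0.5 and 76.9% at 0.8.

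In the 20% case from 67 per arm, overall power matches the stated figure only because Week 1 keeps all 67. The fourth-dose AUC is already at 54 per arm, so visit timing alone has used the whole reserve.

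**The case against.** **Footnote u may already bind.** Read as elapsed time, ±6 hours would keep every compliant sample inside the SAP limit. But the footnote also governs Weeks 12, 20 and 28, whose visits have ±3 or ±7 days, and on that reading those windows would be unusable for PK. Time of day fits Table 1 better. It is the probable reading, not a certain one, and sampling detail is deferred to a Laboratory Manual that is not available here.

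**The loss is unquantified.** A reader might infer that the 81% power will not be delivered. The documents do not support that. If most visits cluster near Day 29 the loss is small, and a 20% loss from all 67 per arm still gives 80.9%. The 36-45% figures need visits spread evenly over seven days, which nothing in the plan suggests. This objection stands against any single power figure, but not against the mismatch.

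**SAP 4.8.1.** A reader might also infer that it contradicts SAP 13.2. It classifies deviations for reporting and allows data points to be excluded after blinded review, whereas 13.2 is the specific rule for parameters. A Day 31 visit is, besides, not a protocol deviation. The two sections are in tension, no more.

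**Reach.** PK is a secondary objective in a sub-population, the ORR analysis is untouched, and excluded AUCs are still calculated and listed. All of this stands and limits the severity.

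**Conclusion.** The mismatch is real and holds on either reference point: 4 of 7 permitted Week 5 days, or 12 of 21 permitted dose/visit pairs, remove a compliant patient from a primary PK comparison. It rests on reading footnote u as time of day.

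The size is an assumption range (CV 38%, no true difference, two independent AUCs). Overall power is about 78% or 85% for a 10% loss, 73% or 81% for a 20% loss, and 36% or 45% for an even spread, starting from 60 or 67 per arm respectively. The plan should be corrected, because following it as written discards usable primary-endpoint data. The documents do not show that the PK comparison will be underpowered.

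**What to change.** Reconcile the two windows before unblinding.

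- **SAP 13.2, late samples.** When the Week 5 sample is within the protocol window but later than 168 h after the actual fourth infusion, derive the AUC to exactly 168 h by log-linear interpolation and keep the patient in the primary comparison. Parameters already use actual elapsed times and a log-down rule, so this fits the existing method.
- **SAP 13.2, early samples.** Samples more than 1 day early need extrapolation, up to 7 − 3 = 4 days, and only the predose, end-of-infusion and Week 5 samples define the curve. Include them in a prespecified sensitivity analysis. Report the present ±1-day rule as a further one.
- **Protocol Table 1 and footnote u, for PK/PD patients still to be sampled.** Time the Week 5 PK sample at 7 days ±1 after the actual fourth infusion, and state that ±6 hours is time of day.
- **SAP 4.8.1.** Cross-refer to the 13.2 timing rule.

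For patients already sampled, interpolation restores the late half of the failing pairs (6 of 12). Under an even spread the primary comparison would then lose 2/7 (29%) and not 4/7, close to the 30% row of the table.

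The cost is minor SAP and programming work, a tighter Week 5 PK window, and reliance on a log-linear decline between the end-of-infusion and Week 5 samples.
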